## **5.0 Inclusion and Exclusion Criteria/ Study Population**

Healthy volunteers of all ethnic and racial categories will be accepted into this study protocol. No preference will be given based on race, gender, or ethnicity. Pregnant persons and children under the age of 18 will be excluded for safety reasons. No vulnerable populations or special classes of subjects will be considered for participation.

### ***Inclusion Criteria***

- Age 18-65
- Have the capacity and ability to provide one's own consent and sign the informed consent document

***Exclusion Criteria***

- Contraindicated for MRI.
- Any current or recent untreated medical, neurological, or psychiatric conditions
- Metal implant devices in the head, heart, or neck.
- History of brain surgery.
- History of myocardial infarction or arrhythmia, bradycardia.
- Personal or family history of seizure or epilepsy or personal use of medications that substantially reduce seizure threshold (e.g., olanzapine, chlorpromazine, lithium).
- Personal history of head injury, concussion, or self-report of moderate to severe traumatic brain injury.
- Individuals suffering from frequent/severe headaches.
- Individuals with a reported history of psychosis or mania, or individuals who are actively manic or psychotic.
- Regular or recent pain medication use
- Moderate to severe alcohol use (>3 drinks/day) or illicit substance use (urine confirmed).
- Persons who are pregnant or lactating

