## 1.0 Objectives / Specific Aims

[figure not shown]
**Aim: Evaluate whether sonicating the Nucleus Accumbens (NAc) with transcranial focused ultrasound modifies functional connectivity between the NAc and the prefrontal cortex (PFC).**

In this single visit, open-label pilot trial, we plan to evaluate whether transcranial focused ultrasound (tFUS), delivered to the nucleus accumbens (NAc) within the magnetic resonance imaging (MRI) scanner will impact resting state functional connectivity between the NAc and functionally connected brain regions like the prefrontal cortex (PFC) and the anterior cingulate cortex (ACC) in up to 10 healthy individuals.

[figure not shown]
**HYPOTHESIS :** tFUS will reduce prefrontal cortex (PFC)-NAc functional connectivity, in healthy individuals. We will investigate this hypothesis by administering tFUS within to MRI scanner to healthy individuals and conduct resting state functional neuroimaging before- and after the tFUS stimulation.

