## 2.0 Background

Currently, several brain stimulation approaches have attempted to modulate pain, mood, and behavior with limited success. The two most studied approaches are transcranial magnetic stimulation (TMS) and transcranial direct current stimulation (tDCS). TMS, which is FDA approved for treating depression and OCD, can only stimulate the surface of the brain and can only stimulate deeper by increasing the intensity, and spreading the field. It is thus not deep and focal but deep and broad. Unlike TMS, which is a cortical stimulation approach, deep brain stimulation (DBS), which is FDA approved for treating Parkinson's Disease (PD), can stimulate deep in the brain with high spatial specificity. DBS has been also investigated experimentally to manage neuropathic pain; however, the surgical risk and implantation of the electrodes are semi-permanent and arguably not worth the benefit. Lastly there is tDCS, a low cost, low-amplitude electric current delivered to the scalp and ultimately through brain. tDCS is not powerful enough to depolarize neurons, although it has been demonstrated to influence the level of excitability and modulate the firing rate of individual neurons. Of all brain stimulation approaches, there is a need for a safe, noninvasive, focal, and effective approach that can reliably modulate neural tissue. This proposal addresses this gap, by advancing transcranial focused ultrasound (tFUS), a technological advancement on the forefront of neuroscience and neuromodulation (Figure 2).

**Functionally connected areas of the Nucleus Accumbens (NAc).** Key emotional, pain, and reward systems are connected through the NAc, including the insula, dorsal anterior cingulate cortex (dACC), prefrontal cortex (PFC), thalamus (Tha), amygdala (Amy), and periaqueductal gray (PAG). Additionally, the NAc receives excitatory inputs from the ventromedial PFC, dACC, amygdala, and hippocampal formation (not shown) and dopaminergic inputs from the ventral tegmental area (VTA) of the midbrain.

[figure not shown]
**Figure 2.** On the right, the electric fields produced by tDCS and TMS are presented. These two commonly utilized forms of brain induce biologically active electrical fields in broad (>4cm) cortical targets. Alternatively, tFUS (right) has the capability to focally deliver energy to cortical and subcortical tissue with <1cm resolution.(33)

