## **4.0 Study Endpoints (if applicable)**

### **Primary Outcome: Neuroimaging/Fronto-Striatal Resting State Functional Connectivity**

The main outcomes of this study are brain imaging related. Using a neuroimaging technique called resting state functional connectivity, which is a statistical dependence between time series of electro-physiological activity and (de)oxygenated blood levels in distinct regions of the brain. Functional connectivity “strength calculation” determines whether the activity between a pair of brain regions covaries or correlates over time. We will investigate the strength of the functional connectivity between the stimulation target (Nucleus Accumbens) and connected areas, including the prefrontal cortex, hippocampus, amygdala, and sensory areas of the brain at baseline, and then will determine whether tFUS increases or decreases the resting-state connectivity between these regions after the NAC has been stimulated.

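### Does the general health exclusion let people with treated conditions into a sample described as healthy?

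*Protocol*

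**What the plan says.** Section 1.0 states the hypothesis for a healthy population: "tFUS will reduce prefrontal cortex (PFC)-NAc functional connectivity, in healthy individuals". Section 5.0 opens with "Healthy volunteers of all ethnic and racial categories will be accepted into this study protocol", and Sections 6.0, 8.0 and 10.0 use the same label. None of them defines the word.

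The Inclusion Criteria set an age range of 18 to 65 and one further requirement: "Have the capacity and ability to provide one's own consent and sign the informed consent document". Neither concerns health, so the exclusions carry that burden. The only general one is "Any current or recent untreated medical, neurological, or psychiatric conditions".

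More specific exclusions stand beside it. Two bear on treated illness: "Individuals with a reported history of psychosis or mania, or individuals who are actively manic or psychotic", and a bar on "personal use of medications that substantially reduce seizure threshold (e.g., olanzapine, chlorpromazine, lithium"), which is joined to personal or family history of seizure. Others cover brain surgery, head injury, frequent or severe headaches, cardiac history, pain medication, heavy drinking and illicit drug use.

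The primary outcome in Section 4.0 is resting-state connectivity of the nucleus accumbens (NAc), measured before and after stimulation. The study "will determine whether tFUS increases or decreases the resting-state connectivity between these regions after the NAC has been stimulated".

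**The concern.** The general exclusion can be read in two ways. If *untreated* governs both *current* and *recent*, which is the more natural reading, someone under treatment for depression or anxiety is not excluded by this line. If it governs only *recent*, every current condition excludes, treated or not. The same volunteer then gets opposite answers, and the steps listed in Section 10.0 (phone screen, urine drug screen, alcohol question, pregnancy test) are not described as settling the matter.

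The subject of the study makes this look more than cosmetic. The Background says that "Key emotional, pain, and reward systems are connected through the NAc", so psychiatric illness bears on the circuit being measured. In a very small sample, one or two such participants could make the group differ from the population for which the result will be reported. If screeners read the line differently, eligibility would also be applied unevenly.

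**Working it through.** The protocol gives no figure to reproduce, because the point concerns wording. The check is to run each type of condition through the general exclusion under both readings and then see what the rest of the protocol does with the cases that differ.

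**Step 1: the general exclusion alone.**

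| Condition | Reading A: *untreated* limits both | Reading B: *untreated* limits *recent* only |
|---|---|---|
| Current, untreated | excluded | excluded |
| Recent, untreated | excluded | excluded |
| Current, treated | not excluded | excluded |
| Recent, treated, no longer current | not excluded | not excluded |

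The readings differ in one row of four, current treated conditions. It would be too broad to say that the second reading bars treated conditions in general, because the last row passes under both.

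**Step 2: the other exclusions.** Within that row, the specific criteria already remove people with a history of seizure or epilepsy, psychosis or mania, head injury, frequent or severe headaches, brain surgery, myocardial infarction, arrhythmia or bradycardia, and users of pain medication. The seizure-threshold drug list is given by example and is therefore open, so some treated volunteers are barred by their drug. What remains is a current treated condition outside all of these, for example depression or anxiety on a drug not judged to lower the seizure threshold substantially.

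**Step 3: the opening of Section 5.0.** An exclusion line admits nobody; it only fails to exclude. The opening sentence says that healthy volunteers are accepted. A screener applying the whole section asks both whether the volunteer is healthy and whether any exclusion applies. The first question is undefined but not empty.

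**Step 4: do neighbouring lines settle the reading?** The line on active mania or psychosis would add little under Reading B, and the drug line does most of its work if treated people can reach it. Both lean towards Reading A. The inference is weak, because the list overlaps elsewhere: metal implants overlap with MRI contraindication, and pregnancy is excluded both in the opening paragraph and in the list.

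**Step 5: effect on the outcome.** Write a participant's connectivity as a personal level *a* plus, after stimulation, a response *d*. The change is (*a* + *d*) − *a* = *d*. A condition that alters only the stable level *a* cancels. Only a different response *d* would matter, and the protocol gives no value for one and no evidence that one exists.

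**Step 6: share of the sample.** Section 6.0 allows up to 10 participants, so one person is 1/10 = 10% of a full sample. Sections 3.0 and 10.0 speak of active or sham sessions. If the sample were split equally (an assumption, since no ratio is stated), one person would be 1/5 = 20% of an arm. These are shares, not biases. Turning them into a shift in the mean would need an assumed difference in response, for which the protocol offers no basis.

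**The case for a change.** The strongest case for acting is that eligibility is fixed in the protocol, is applied by screeners and cannot be left to a later analysis plan. The line does have two readings, nothing in the document chooses between them, and the repeated label does not define itself. Rewording one line would cost almost nothing. All of that stands.

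What does not follow is that the plan is wrong. The document nowhere equates healthy with free of any treated condition, so even Reading A does not contradict it. Accepting people whose illness is treated, while turning away those whose illness is not, is a defensible design; so is barring both. Rewordings of the line could go in opposite directions. One that barred recent or current neurological and psychiatric conditions whether treated or not would add a restriction found in neither reading, because recent treated conditions pass under both. Uneven screening is conceivable, but the content of the phone screen is not given, so it remains conjecture.

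**Conclusion.** No change to the plan is called for. This is a gap in wording that the study team can fill sensibly by applying one reading at the existing phone screen and describing the enrolled participants accurately when reporting. It affects one category, current treated conditions not caught by another exclusion.

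One such participant would be at most a tenth of a full sample of 10, or a fifth of an arm under an assumed equal split. No consequence for the connectivity result can be derived from the document; it is nil if those participants respond to sonication as the others do. The conclusion rests on two points: the outcome is a within-person change, and the document contains no evidence of a different response in treated participants. A clearer sentence would be welcome if the protocol is revised for another reason, but no stated rule has been shown to give a wrong result.

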**6.0 Number of Subjects**

We will enroll up to 10 healthy adults for this study.

**7.0 Setting**

All participants will complete the study tasks on at the MUSC [name] Center for Biomedical Imaging. Subjects will be consented and educated about the study in a private screening area within the [name] center. tFUS will be administered within the MRI scanner.

**8.0 Recruitment Methods**

Healthy participants will be recruited from the MUSC community (students and staff) as well as general population from the greater Charleston region. We will recruit via word of mouth and flyers.

**9.0 Consent Process**

Consent procedures will be conducted in a private, quiet room at the MUSC [name] Center for Biomedical Imaging. Approved study personnel will walk through the consent procedures with the participant. Furthermore, after the consenting procedures, the consent form will be printed and provided to all participants to independently review to ensure understanding, including describing the laboratory measures, study duration, and equipment and materials. The study team will describe confidentiality/privacy measures, participant right to withdraw, risks/benefits, and that up to \$100 compensation will be provided. In addition, participants will be prompted to ask questions throughout consenting to further ensure understanding. After signing the consent form, they will also be offered a hard copy.

## 10.0 Study Design / Methods

- *Study Overview:* After determining eligibility and interest, written informed consent will be obtained from participants at the MUSC Center for Biomedical Imaging. Enrolled participants will be placed into the 3T MRI outfitted with a concurrent tFUS plus fMRI acquisition system (Brainsonix). First, participants will have baseline resting state functional neuroimaging conducted to quantify the functionally connected areas to the nucleus accumbens. Afterwards, while still in the MRI scanner, we will administer tFUS to the nucleus accumbens. Lastly, we conducted post-tFUS neuroimaging (same as pre-tFUS). This entire MRI procedure will take approximately 1 hour. Participants will be compensated \$100 for their time.
- *Recruitment, Screening, and Consent Procedures:* Healthy participants will be recruited from the MUSC community (students and staff) as well as general population from the greater Charleston region. We will recruit via flyers around campus, e-mail announcements and word of mouth. If interested in learning more about the study, potential subjects will be phone screened and educated regarding the study's details. If interested in participating in the study, they will be consented and enrolled into the study's protocol. We then will conduct a multi-panel urine drug screen to confirm they are not using illicit drugs and ask for their alcohol consumption (>3 drinks per day is exclusionary).
- *Pregnancy Test Procedures:* If participants are individuals biologically capable of becoming pregnant, they will be provided with a pregnancy test strip. After completing the pregnancy test, participants with negative results will be asked to continue to the remaining study procedures, whereas those with a positive result will be debriefed and released.
- *tFUS Procedures:* All tFUS will be administered in similar mythology to that in our prior published work (25). Within the MRI scanner, participants receive two, 10-min sessions of either active or sham tFUS spread 10 min apart targeting the nucleus accumbens [fundamental frequency: 650 kHz, Pulse repetition frequency: 10 Hz, Pulse Width: 5 ms, Duty Cycle: 5%, Sonication Duration: 30s, Inter-Sonation Interval: 30 s, Number of Sonifications: 10, ISPTA.0 995 mW/cm^2, ISPTA.3 719 mW/cm^2, Peak rarefactional pressure 0.72 MPa].
- *Sham tFUS Procedures:* Participants will be randomized to receive either two, 10 minute active tFUS sessions, or two 10 minute sham tFUS sessions within the scanner. The sham sessions will include a transducer that is connected in a similar fashion to that of active tFUS, however the cable will not be plugged into the system, thus no ultrasound will be delivered to the participant. Participants will not know or be told whether they are receiving active- or sham- tFUS.
- *Neuroimaging Procedures:* All MRI imaging will be performed using a Siemens 3.0 T Prisma scanner equipped with a 32-channel head coil. MRI data will be acquired from all participants before and after tFUS administration. All MRI scan visits will be held at the MUSC Center for Biomedical Imaging (CBI; see the Facilities and Resources section). Each MRI scan session will include a high-resolution T1-weighted structural scan (whole brain sagittal acquisition, 224 slices, TR=2530ms,

TE=3.65ms, TI=1100ms, 1mm thick slices, FOV=256, 256x176, flip angle = 7 degrees.), followed by 24 minutes of resting-state scanning, then a concurrent tFUS/fMRI paradigm, and lastly, 24 more minutes of post-tFUS resting-state scanning. All functional scans will use the high-resolution fMRI protocol described in the Preliminary Study: whole brain acquisition, 136 axial slices, 1.5x1.5x1.5mm voxel size, TR=2000ms, TE=30ms, FOV=204mm, multi-band factor=3.

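### Does the one-hour estimate for the MRI procedure, which is shorter than its listed components, call for a change to the plan?

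*Protocol*

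**What the plan says.** All the timings stand in the protocol, almost all in Section 10.0 Study Design / Methods.

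- **Total.** The Study Overview describes baseline imaging, tFUS and post-tFUS imaging, then states: "This entire MRI procedure will take approximately 1 hour".
- **Imaging blocks.** The Neuroimaging Procedures bullet begins with anatomy ("Each MRI scan session will include a high-resolution T1-weighted structural scan"), "followed by 24 minutes of resting-state scanning, then a concurrent tFUS/fMRI paradigm, and lastly, 24 more minutes of post-tFUS resting-state scanning".
- **Stimulation.** The tFUS Procedures bullet gives "two, 10-min sessions of either active or sham tFUS spread 10 min apart", with the parameters "Sonication Duration: 30s, Inter-Sonation Interval: 30 s, Number of Sonifications: 10". The Sham tFUS Procedures bullet repeats the session count and length for both arms: "two, 10 minute active tFUS sessions, or two 10 minute sham tFUS sessions within the scanner".
- **One sitting.** Section 1.0 opens its description of the study with "In this single visit, open-label pilot trial". The Study Overview adds: "Afterwards, while still in the MRI scanner, we will administer tFUS to the nucleus accumbens".

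**The concern.** The overview's total is meant to cover the whole MRI procedure, yet the two resting-state scans alone use 48 minutes of it. That leaves 12 minutes for stimulation that needs at least 20. Because this is a single visit and tFUS is given without leaving the scanner, the excess cannot be moved to another day or outside the MRI time.

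Two things could be at stake. The first is participant burden: if the hour is what participants are told or what is booked, it is too short. The second is more statistical. The last block is the post-tFUS scan, so if the hour were enforced as a fixed slot, that scan would lose the time. The primary outcome compares connectivity before and after stimulation, and a shortened second scan would make the two measurements unequal in length.

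**Working it through.** **Inputs** (Section 10.0): resting-state scan before tFUS 24 min; resting-state scan after tFUS 24 min; two tFUS sessions of 10 min; separation 10 min, which can mean a pause between sessions or the time from start to start; stated total about 60 min.

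**Session length from the sonication parameters.** Ten sonications of 30 s, each followed by a 30 s interval: 10 × (30 + 30) s = 600 s = 10 min, which agrees with the stated session length. If the interval after the last sonication is dropped: 10 × 30 + 9 × 30 = 570 s = 9.5 min.

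**Total = rest before + 2 × session + pause + rest after.**

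| Reading | Sum (min) | Total (min) | Over 60 min |
|---|---|---|---|
| 10-min sessions, back to back | 24 + 20 + 0 + 24 | 68 | 8 (13%) |
| 10-min sessions, 10-min pause | 24 + 20 + 10 + 24 | 78 | 18 (30%) |
| 9.5-min sessions, back to back | 24 + 19 + 0 + 24 | 67 | 7 (12%) |
| 9.5-min sessions, 10-min pause | 24 + 19 + 10 + 24 | 77 | 17 (28%) |

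The stated hour is therefore not reproduced. Letting 10 minutes of the second resting-state scan fall inside the pause brings 78 only back to 68. A single 10-minute session would fit (48 + 10 = 58 min), but the tFUS and sham bullets and Section 3.0 all specify two.

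**Structural scan.** It belongs to the session, but its duration is not given, so it is left out of the totals. It can only lengthen them. Positioning and set-up have no stated time either and are not counted.

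**What depends on the hour?**

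- Primary outcome (Section 4.0): connectivity between the nucleus accumbens and connected regions at baseline and after stimulation. It uses the scans themselves, not the total time.
- Sample size (Section 6.0): up to 10, with no link to session length.
- Comparison between arms: the sham bullet gives both arms the same two 10-minute sessions, so a longer visit affects both alike.
- Equality of the two scans: if the hour were a hard limit, the second scan would shrink to 24 − 8 = 16 min or 24 − 18 = 6 min. But the protocol calls the hour approximate, gives both scans as 24 minutes, and says in the Study Overview that post-tFUS imaging is the same as before. Nothing there lets staff cut a scan to meet the estimate.

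**The case for a change.** The strongest case for acting is that 68 minutes is a floor. It takes the less natural reading of the 10-minute separation and allows no time for a structural scan that the protocol requires. With a real pause the figure is 78 minutes plus that scan, which is hard to call about an hour. Section 10.0 gives the only total for the MRI procedure, Section 9.0 says that study duration is described at consent, and a correction would cost one line.

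The arithmetic in this case stands in full, and the wording of the separation is open to two readings that differ by 10 minutes in total length. Three things weaken the conclusion drawn from it.

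- The direction of the error is unknown. A misprinted block length would produce the same mismatch, so the protocol supports saying that the figures disagree but not that the hour must be raised.
- The link to consent cannot be shown. The form is not available, and the duration in it may well be right.
- No harm to the inference has been identified. Those who book and run the scans work from the listed sequences and sessions, not from the overview's estimate.

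**Conclusion.** The concern is correct as arithmetic but does not call for a change to the plan. The stated hour falls short of the listed components by 8 minutes (13%) with sessions back to back or 18 minutes (30%) with a 10-minute pause, taking 10-minute sessions as stated and leaving out the structural scan. The word approximately loosely covers the lower figure but not the higher one.

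This is a clerical inconsistency between a rounded overview estimate and the specific timings in the same section. Correcting it would alter no endpoint, sample size, analysis or conclusion. That judgement rests on the block lengths, not the hour, governing what is acquired, which is how the section reads. If the protocol is revised for another reason, the total and the component times should be reconciled; nothing here shows which of them is wrong.
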